7.3 Randomization and Blinding

Subjects will be randomly assigned in a 1:1 ratio to 1 of the 2 treatment arms. Subjects must be randomly assigned to study treatment within 120 days of completing surgery and start treatment within 1 week of randomization. (Note: only under certain unforeseen circumstances that are not caused by noncompliance or inappropriate planning [eg, adverse weather], randomization may occur after day 120 from definitive surgery but window for randomization and dosing should be 127 days total (120 days +7 days). Randomization will be stratified by lymph node involvement (yes vs no), prior neoadjuvant cisplatin chemotherapy (yes vs no), Stage (pT2 vs >pT2), and disease type (UTUC vs UBC). The number of subjects refusing cisplatin-based perioperative therapy will be capped at approximately 10% of the total population (approximately 22 subjects), no more than 15% of the population will be enrolled with UBC, and ≤25% of UTUC subjects will have Stage pT2 UTUC (limit will be based on stratification). Documented medical monitor approval is required before randomization. Interactive Response Technology (IRT) will be used to assign subjects to treatment based on the stratification factors entered into the system. Site personnel will be given a unique subject number for each subject, consisting of a unique center number followed by a sequential subject number suffixed to it.

This is a double-blind study. Subjects, Investigators, study monitors, and the study team will be blinded to the treatment administered, except for a designated QED Clinical Supply representative. Staff associated with tracking, assaying, and analyzing PK samples may have access to the PK-related information only, and the contract research organization (CRO) analyzing PK samples for concentration will be unblinded to study treatment.

Treatment assignment may be unblinded by the sponsor/designee to satisfy expedited safety reporting requirements of regulatory authorities. If an SAE report meets expedited safety reporting criteria, the sponsor's safety representative or designee will unblind the study treatment for the respective patient for regulatory reporting purposes.

Emergency unblinding: Treatment unblinding by the investigator should be conducted in an emergency only when knowledge of the treatment assignment will affect the management of a subject who experiences a treatment-emergent AE. The investigator will have the ability to perform emergency unblinding. The knowledge of the actual treatment the unblinded subject received should be concealed from any site-level (including any party involved in subject assessment, for example, ophthalmologist) or sponsor (and their representative) personnel involved in managing subject's data, in order to protect ongoing data acquisition and interpretation.

The sponsor recognizes, however, that unblinding for nonemergency situations will be of increasing concern to many sites as additional treatment options become available for subjects who have recurrence of their urothelial carcinoma by BICR. For such subjects, single-subject unblinding in nonemergency situations may be performed by the study team only with medical monitor approval for the purpose of facilitating subsequent treatment decisions, including assessment of eligibility for other clinical trials.

The process of unblinding in these circumstances will require written request submitted to medical monitor (sponsor or representative) with reason for the unblinding request. The nonemergency unbinding may occur only with written approval by the medical monitor.

Including for these cases of nonemergency unblinding, the knowledge of the actual treatment the unblinded subject received should be concealed from any site-level (including any party involved in subject assessment, for example, ophthalmologist) or sponsor (and their representative) personnel who continue to manage patient's data in order to protect ongoing data acquisition and interpretation

The investigator must notify the medical monitor or designee after determining it is necessary to unblind a subject's treatment assignment. The investigator must also indicate in source documents and in the eCRF that the blind was broken and provide the date and reason for breaking the blind. Any AE or SAE associated with breaking the blind must be recorded and reported as specified in this protocol.

In order to limit the number of individuals with access to the unblinded information, Investigators or dedicated study personnel should handle this information with highest confidentiality. Any documentation regarding the treatment assignment should be kept in an envelope, securely stored, and not attached to the subject's files in order to allow for unbiased/blinded continuation of subject's evaluation, and the information should not be communicated or distributed to any personnel other than those who need to know for subject management.

Unblinding of study treatment should not result in withdrawal of the subject from the study, and these subjects will continue to be followed per the protocol.

The investigator can unblind treatment via the IRT system. The investigator should document all occurrences of unblinding in the study file and the reason for unblinding should be documented.

If the investigator would like to discuss the subject's treatment assignment (once known) with the sponsor, the site may liaise with the unblinded Global Study Manager (GSM). The investigator is to communicate directly with the unblinded GSM via email at:

[contact]. The unblinded GSM will then convey any discussions to the medical monitor in a "blinded" fashion for any case that requires medical input. If there is an urgent question pertaining to subject management, the site should call the medical monitor but not disclose treatment assignment or unblinding status unless specifically requested.

7.4 Compliance

The investigator or responsible site personnel should instruct the subject to take study drug exactly as prescribed to promote compliance. All dosages prescribed and dispensed to the subject and all dose changes or missed doses during the study must be recorded on the appropriate eCRF as outlined in the Case Report Completion Guidelines. Subject re-training for dosing non-compliance should be conducted and documented, as needed.

Subjects will be instructed to return all used and unused bottles of study drug to the study center at the end of each cycle and at the end of the study or at the time of discontinuation of study drug. Compliance will be assessed by the investigator and/or study personnel, and compliance information will be captured in the Drug Accountability Form. This information must be captured in the source document at each subject visit.

7.5 Supportive Care Guidelines

Any supportive care for disease related symptoms, including any medication or therapy for a concurrent medical condition are permitted, except if specifically prohibited below.

7.5.1 *Hematopoietic Growth Factors*

Hematopoietic growth factors (eg, erythropoietin [EPO], granulocyte colony-stimulating factor (G-CSF), granulocyte-macrophage colony-stimulating factor [GM-CSF]) and blood transfusions are not to be administered prophylactically or to be used to meet eligibility criteria. However, these drugs may be administered according to the label of these agents or as dictated by local practice or guidelines established by the American Society of Clinical Oncology (ASCO), European Society of Medical Oncology (ESMO), or other appropriate regional societies.

7.5.2 *Management of Hyperphosphatemia*

Hyperphosphatemia is a recognized on-target effect of potent and selective inhibitors of the FGFR pathway. While on study drug, subjects should avoid foods that are especially high in phosphate and, if possible, should restrict dietary phosphate to 600 – 800 mg/day. High-phosphate foods include dairy products; meats, nuts, and other high-protein foods; processed foods; and dark colas. Phosphorus will be checked at screening and starting on Cycle 1 Day 4. Subjects who experienced hyperphosphatemia should take a phosphate binder such as sevelamer, sacroferric oxyhydroxide, lanthanum carbonate, ferric citrate, etc. within 30 minutes of a meal on the day while taking study drug. Once the subject has had hyperphosphatemia, the subject should

remain on a low phosphate diet, if possible, and take phosphate binder on the days study drug is taken even, if the serum phosphorus is normalized. Unless otherwise specified by the local prescribing information or institutional practice, the following regimen should be used to manage hyperphosphatemia:

- For serum phosphorus $>5.5 - \leq 7.5$ mg/dL
 - Start sevelamer 800 mg 3-times per day with meals
 - Increase the dose of sevelamer up to 1200 mg every 8 hours
- For serum phosphorus >7.5 mg/dL
 - Increase the dose of sevelamer up to 1600 mg (2 tablets per meal) every 8 hours
 - Consider adding acetazolamide, 2 to 3 tablets (250 mg) per day

During the study drug cycle, subjects do not need to be on a low phosphate diet or take a phosphate binder during their 1 week off study treatment period (Days 22-28 of cycle) unless serum phosphate is not normalized. Other dose modifications for hyperphosphatemia are provided in [Table 6](#), but should be modified as per country or institutional practice.

7.5.3 *Management of Diarrhea*

Study drug dose modification recommendations are provided in [Table 6](#). Subjects should be instructed to notify their physician immediately at the first signs of poorly formed or loose stool or an increased frequency of bowel movements. Administration of antidiarrheal/antimotility agents is recommended at the first sign of diarrhea as initial management. Some subjects may require concomitant treatment with >1 antidiarrheal agent. When therapy with antidiarrheal agents does not control the diarrhea to tolerable levels, study treatment should be temporarily interrupted or dose reduced ([Table 5](#)).

7.5.4 *Management of Alopecia, Palmar-Plantar Erythrodysesthesia Syndrome, Paronychia, and Stomatitis*

Recommendations for management (not required per protocol) of stomatitis (adapted from [Rugo 2017](#)), PPES, paronychia (adapted from [Segaert 2005](#)), and alopecia are provided in [Table 7](#). These recommendations and the additional information provided below, which includes management of dry skin and dry mouth/xerostomia (adapted from [Lacouture 2020](#)), are guidelines only and institutional guidelines should be followed where applicable.

In addition, as a general guideline, if toxicity is tolerable and treated, study treatment may be continued for Grade 1 and Grade 2 AEs and interrupted for Grade 3 AEs; rechallenge at a reduced dose may be initiated when dermatologic events improve to Grade ≤ 1 or baseline or for a well-tolerable Grade 2 toxicity.

Table 7: Management of Skin Toxicity

SKIN AND SUBCUTANEOUS TISSUE DISORDERS	
Alopecia	
Grade 1	Continue study drug 
 • Minoxidil 5% (OTC) solution or foam once daily to scalp
Grade 2	Continue study drug 
 • Minoxidil 5% (OTC) solution or foam twice daily to scalp • Fluocinonide 0.05% solution daily to scalp
Palmar-plantar erythrodysesthesia syndrome	
Grade 0/1	Continue study drug 
 • Urea 20% or ammonium lactate 12% lotions BID to hands and feet
Grade 2	Continue study drug 
 • Urea 20% or ammonium lactate 12% BID to hands and feet • Fluocinonide 0.05% cream BID to hands and feet
Grade 3	Hold study drug until resolved to Grade ≤ 1 
 • Urea 20% or ammonium lactate 12% BID to hands and feet • Fluocinonide 0.05% cream BID to hands and feet
Paronychia	
Grade 1	Continue study drug 
 • Clindamycin 1% solution around and under nails TID • Soak for 15 minutes daily in white vinegar in tap water (1:1) • Topical povidone iodine 2%–10% applied BID
Grade 2	Continue study drug 
 • Obtain bacterial cultures to confirm sensitivity to antimicrobial • Cefadroxil 500 mg BID or TMP/SMX DS BID for 14 days • Soak for 15 minutes daily in white vinegar in tap water (1:1) • Topical povidone iodine 2%–10% applied BID • Dermatology consultation
Grade 3	Hold study drug until resolved to Grade ≤ 1 
 • Obtain bacterial cultures to confirm sensitivity to antimicrobial • Cefadroxil 500 mg BID or TMP/SMX DS BID for 14 days • Dermatology consultation
Stomatitis	
Grade 1/2	Continue study drug 
 • Dexamethasone elixir 0.5 mg/mL swish and spit 1 teaspoon (5 mL) TID.
Grade 3	Hold study drug until resolved to Grade ≤ 1 
 • Dexamethasone elixir 0.5 mg/5 mL swish and spit 1 teaspoon (5 mL) TID. • Clotrimazole 10 mg lozenges 3-5 times/day

Abbreviations: BID=2 times daily; OTC=over-the-counter; TID=3 times daily; TMP/SMX DS=sulfamethoxazole and trimethoprim.

Additional guidelines for specific skin toxicities:

- Alopecia: hair camouflaging methods (such as TOPPIK™) may be considered. Alopecia typically reverses when treatment is discontinued.
- PPES: Prevention strategies for PPES include prophylactic removal of hyperkeratotic areas, application of moisturizing cream containing urea $\geq 10\%$, pedicures, and cushioning of callused areas. Other preventive tactics include avoiding activities that cause force or rubbing on the hands and feet during the first 6 weeks of treatment and limiting contact with harsh chemicals and sources of heat (eg, saunas, sun exposure).

- Stomatitis: Preventive strategies may include dental work to eliminate existing tooth and gum disease before starting treatment and education regarding the importance of thorough and frequent cleaning of the oral cavity. Avoiding salty, spicy, or citrus-based foods, and hot beverages may help prevent stomatitis.
- Dry skin: Subjects should be advised to moisturize skin and avoid excessive exposure to detergents and soaps containing fragrances. Urea preparations have been shown to prevent transepidermal water loss, and salicylic acid preparations are helpful due to their keratolytic, bacteriostatic, and fungicidal properties. Exfoliation of scaly areas of xerosis is recommended. More severe grade 3 xerosis, which can result in asteatotic dermatitis, can be treated with low-potency topical steroids (eg, hydrocortisone 2.5% cream or ointment, triamcinolone 0.1% cream).
- Dry mouth/xerostomia: The importance of good oral hygiene, regular dentist visits, and other strategies for preventing oral disease should be stressed. Toothpaste with high fluoride content is recommended to prevent cavities. Treatment may include systemic and topical salivary stimulants (eg, cevimeline and pilocarpine, and intraoral topical agents, such as chewing gums and saliva stimulants and substitutes).

7.5.5 *Management of Dry Eye and Blurred Vision*

For management of dry eyes and/or blurred vision, the following supportive measures can be implemented singly or in combination and as advised in consultation with an ophthalmologist:

- 1) Artificial tears, 4 times per day.
- 2) Artificial tears without preservative, 6 times per day.
- 3) Ointments (any over-the-counter or Vaseline®).
- 4) Steroid drops (prescription; may help with corneal haze).
- 5) Punctal plugs (requires ophthalmologist management).

7.6 *Prior and Concomitant Medications*

At Screening, subjects are to be asked about their history of prior medication (including prior antineoplastic therapy); Investigators are to check for use of any disallowed prior medications, as outlined in the Exclusion Criteria for the study (Section 6.2).

For each subject enrolled in the study, all anticancer therapies ever taken for urothelial carcinoma and other medications taken within 28 days of first dose of study drug are to be recorded on the appropriate page of the eCRF.

All prescription and non-prescription medications administered from the time of first dose of study drug through 30 days after last dose are to be recorded for each subject on the appropriate page of the eCRF. Dates for the start and stop of each concomitant medication are to be recorded, as well as the reason for administration (particularly if administered for an AE). Any changes in dose of concomitant medications are to also be recorded.

Cancer medications taken by the subject after last dose of study drug are to be recorded on the appropriate page of the eCRF. Non-medication cancer therapies and surgeries are to be recorded on the appropriate page of the eCRF.

Hormone replacement therapies such as thyroid and growth hormones are allowed, as well as estrogen replacement hormone treatment.

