3.4.2 Clinical Safety

The majority of Study CBGJ398X2101 subjects (99.0%) evaluable for safety experienced ≥ 1 adverse event (AE), with a Grade 3/4 AE reported in 58.7%, regardless of study treatment relationship ([CBGJ398X2101 Clinical Study Report; Pal 2018](#)). The incidence of Grade 3/4 AEs was similar at the MTD (52.6%). The majority of these subjects (95.7%) experienced ≥ 1 AE suspected to be study treatment related, with Grade 3/4 AEs suspected to be study treatment related reported in 38.0%. The incidence of Grade 3/4 AEs suspected to be study treatment related (38.0%) was similar at the MTD (31.6%).

The most common AEs (occurring in $\geq 30\%$ of all subjects, all grades), regardless of study treatment relationship were: hyperphosphatemia (65.4%), constipation (39.9%), decreased appetite (37.5%), fatigue (36.1%), stomatitis (34.1%), and nausea (32.2%). The most common AEs suspected to be study treatment related (occurring in $\geq 30\%$ of all subjects, all grades) were: hyperphosphatemia (63.5%) and stomatitis (33.7%).

The most commonly reported Grade 3/4 AEs (in $\geq 4\%$ of all subjects), regardless of study treatment relationship were: hyperlipasemia (6.7%), hypophosphatemia (6.3%), ALT elevation (5.3%), hyperphosphatemia (4.8%), and fatigue (4.8%). The most frequently occurring Grade 3/4 AEs suspected to be study treatment related (in $\geq 4\%$ of all subjects) were: hyperlipasemia (5.8%), hyperphosphatemia (4.8%), and ALT increased (4.8%).

A total of 57 deaths (27.4%) occurred during the study, and most of these deaths were due to disease progression (24.0%). Of the total deaths, 11.1% were on-treatment deaths; of these, 8.6% subjects died due to disease progression, 2 subjects died due to sepsis, and 1 subject each died due to respiratory failure, cardiac arrest, and unknown reason.

At least 1 serious adverse event (SAE) (occurring in $\geq 5\%$ subjects) of any grade, regardless of study treatment relationship, was reported in a total of 37.5%, with a similar incidence reported at the MTD (40.4%). SAEs suspected to be drug-related were reported in 8.6% of subjects. The most commonly reported SAEs, by preferred term (occurring in $\geq 5\%$ subjects) were: general physical health deterioration (2.9%); pneumonia (2.9%); vomiting (2.9%); dyspnea (2.4%); and, hypercalcemia (2.4%).

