Study drug	125 mg or matching placebo	100 mg or matching placebo	75 mg or matching placebo	50 mg or matching placebo

^a Dose reduction to 50 mg requires prospective sponsor medical monitor approval. Details are provided in the text above.

NOTE: The minimum daily dose of study drug allowed in the study is 50 mg.

Table 6: Criteria for Interruption and Re-initiation of Study Drug for Adverse Events Considered to be Possibly Related to Study Drug

Worst Toxicity CTCAE^a (version 5.0) Grade (Unless Otherwise Specified)	Dose Modifications any Time During a Cycle of Therapy
CARDIAC DISORDERS	
Cardiac – Prolonged QTcF Interval	
Grade 2: Average QTc 481 - 500 msec	
Maintain dose level of study drug.
 
Two additional ECGs separated by \geq5 minutes should be performed to confirm the finding. If the finding is confirmed, single ECG assessments should be performed for 2 additional cycles at the same frequency as in Cycle 1, or as clinically indicated. If abnormality is detected, 2 additional ECGs separated by at least 5 minutes should be performed to confirm the finding.
 
• If ECG assessments show no QTcF \geq481 msec, for subsequent cycles ECG monitoring will be performed according to the visit schedule.• If ECG assessments are still abnormal (QTcF \geq481 msec and \leq500 msec), then ECG monitoring must continue at the same frequency as in Cycle 1 for all subsequent cycles.

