Grade 4 (ANC <500/mm ³ [$<0.5 \times 10^9/L$])	Hold dose of study drug until resolved to CTCAE Grade \leq 1, then \downarrow 1 dose level of study drug. If not resolved within \leq 14 days, discontinue study drug.
Febrile Neutropenia	
Grade 3 (ANC <1000/mm ³ with a single temperature of $>$ 38.3°C [101.0°F] or a sustained temperature of \geq 38.0°C [100.4°F] for $>$ 1 hour)	Hold dose of study drug until resolved to CTCAE Grade \leq 1, then 
If resolved within \leq14 days, \downarrow 1 dose level of study drug.If not resolved within 14 days, discontinue study drug
Grade 4	Discontinue study drug.
Anemia	
Grade 3 (hemoglobin <8.0 g/dL [$<4.9 \text{ mmol/L}$; $<80 \text{ g/L}$]; transfusion indicated)	Hold dose of study drug until resolved or corrected to CTCAE Grade \leq 1 or baseline, then maintain dose level.
Grade 4	Hold dose of study drug until resolved or corrected to CTCAE Grade \leq 1 or baseline, then \downarrow 1 dose level.
Platelet Count Decreased (Thrombocytopenia)	
Grade 3 (platelet <50,000 - 25,000/mm ³ [$<50 - 25 \times 10^9/L$])	Hold dose of study drug until resolved to CTCAE Grade \leq 1 or baseline, then 
If resolved within \leq7 days, maintain dose level of study drug.If resolved between $>$7 days and 14 days, \downarrow 1 dose level of study drug.If not resolved within \leq14 days, discontinue study drug.

Worst Toxicity CTCAE^a (version 5.0) Grade (Unless Otherwise Specified)	Dose Modifications any Time During a Cycle of Therapy
Grade 4 (platelet <25,000/mm ³ [$<25 \times 10^9/L$])	Hold dose of study drug until resolved to CTCAE Grade ≤ 1 or baseline, then \downarrow 1 dose level. 
• If not resolved within ≤ 14 days, discontinue study drug.
INVESTIGATIONS – RENAL	
Serum Creatinine	
Creatinine clearance <30 mL/min (calculated or measured)	Hold dose of study drug until creatinine clearance is ≥ 45 mL/min regardless of grade.
Serum creatinine increase Grade 2 ($\geq 1.5 - 3.0 \times$ ULN or $1.5 - 3.0 \times$ baseline)	Hold dose of study drug until resolved to Grade ≤ 1 or baseline, then: 
• If resolved within ≤ 7 days, maintain dose level of study drug.• If resolved between >7 days and 14 days, \downarrow 1 dose level of study drug• If not resolved within ≤ 14 days, discontinue study drug.

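### Table 7 recommends a five-fold stronger dexamethasone rinse for Grade 1/2 stomatitis than for Grade 3, probably through a dropped digit (minor)

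*Protocol*

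**What the plan says.** Table 7 in Protocol Section 7.5.4 sets out management of skin and mucosal toxicity by grade. It has two stomatitis rows:

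- Grade 1/2: continue study drug and give "Dexamethasone elixir 0.5 mg/mL swish and spit 1 teaspoon (5 mL) TID".
- Grade 3: hold study drug until the event resolves to Grade 1 or lower, give "Dexamethasone elixir 0.5 mg/5 mL swish and spit 1 teaspoon (5 mL) TID", and add clotrimazole lozenges.

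The section introduces the table as "Recommendations for management (not required per protocol) of stomatitis" and the other listed toxicities. It adds that the advice given there and in the accompanying text "are guidelines only and institutional guidelines should be followed where applicable".

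Section 3.4.2 gives the Phase 1 background. The most common adverse events of any grade include "fatigue (36.1%), stomatitis (34.1%), and nausea (32.2"%). The Grade 3/4 events reported in at least 4% of subjects are "hyperlipasemia (6.7%), hypophosphatemia (6.3%), ALT elevation (5.3%), hyperphosphatemia (4.8%), and fatigue (4.8"%). Stomatitis is not in that second list.

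**The concern.** The two rows name the same product, volume and frequency and differ only in concentration: the Grade 1/2 row is per mL and the Grade 3 row is per 5 mL. Read literally, treatment weakens as the toxicity worsens. Nothing else in the protocol or SAP explains this.

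This is a drug strength in a table that sites use to manage patients. A site without its own stomatitis guideline would have reason to follow the printed figure. Antifungal cover is listed only in the Grade 3 row, so the row with the stronger steroid has none. At stake is a mild, avoidable excess of topical steroid in whichever subjects receive the rinse. The trial's inference is not at stake.

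**Working it through.** **Dose per rinse and per day.** All inputs are from Table 7.

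| Row | Concentration | Volume | Per rinse | Per day (three times) |
|---|---|---|---|---|
| Grade 1/2 | 0.5 mg/mL | 5 mL | 0.5 × 5 = 2.5 mg | 2.5 × 3 = 7.5 mg |
| Grade 3 | 0.5 mg/5 mL = 0.1 mg/mL | 5 mL | 0.1 × 5 = 0.5 mg | 0.5 × 3 = 1.5 mg |

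Ratio: 2.5 / 0.5 = 5. This needs no assumption. If the Grade 1/2 row is read as 0.5 mg/5 mL, both rows give 0.5 mg per rinse and 1.5 mg/day, and the ratio is 1.

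**Does the table vary strength by grade elsewhere?** These products recur across grades of one toxicity:

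- Alopecia: minoxidil is 5% at both grades. Only its frequency rises, from once to twice daily, and a topical steroid is added.
- Palmar-plantar erythrodysesthesia: urea 20% or ammonium lactate 12% at every grade; fluocinonide 0.05% cream at Grades 2 and 3.
- Paronychia: povidone iodine 2%–10% at Grades 1 and 2; cefadroxil 500 mg at Grades 2 and 3.

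Each keeps its strength. Dexamethasone is the only one whose strength changes, and it falls as severity rises.

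**Which row would be used more?** From Section 3.4.2, stomatitis of any grade occurred in 34.1% of Phase 1 subjects. Its absence from the Grade 3/4 list means fewer than 4% had it at those grades, taking that list as complete. So more than 34.1 − 4.0 = 30.1% had stomatitis of at most Grade 2. That is more than 30.1 / 34.1 = 88% of the subjects with stomatitis.

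**The case against.** The strongest reply is that this is an editorial slip in optional guidance. The table is not binding, institutional guidelines apply where they exist, and the rinse is spat out. The study-drug instructions in the two rows (continue, hold) do not depend on the rinse strength. The SAP (Section 8.10.2) summarises concomitant medications by class and preferred term, so the strength enters no planned summary. All of this stands and sets the severity at minor. It does not reconcile the two rows.

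A second reply is that the rows are different regimens, since Grade 3 also holds study drug and adds clotrimazole, and that the advice is adapted from a cited trial not available here. This also stands in part: a deliberate inversion is unlikely but not excluded, and the intended strength has to be confirmed by the clinical team.

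Three stronger readings are tempting.

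- A reader might infer that 0.5 mg/5 mL is established as correct. It is only the likelier figure, from the shared 0.5 and 5 mL and from the pattern in the rest of the table.
- A reader might apply the Phase 1 rates to the planned arms and project a number of affected subjects. Those rates pool 208 subjects over nine dose levels and three schedules (Section 3.4). The rinse is optional, and the SAP Introduction records that only a limited number of patients were randomized. A count would not be supported.
- A reader might see a matching error in Table 6, whose title is "Criteria for Interruption and Re-initiation of Study Drug for Adverse Events Considered to be Possibly Related to Study Drug". Its row for clearance below 30 mL/min reads "Hold dose of study drug until creatinine clearance is" at least 45, while exclusion 13c permits entry from 30 if creatinine is within its limit. The documents do not show this to be a mistake. A fixed floor is consistent with the animal renal findings (Section 3.3), the Phase 1 dose changes for hypercreatininemia (Section 3.4.2) and the higher exposure in renal impairment (Section 3.5.3). Section 7.2.5.1 already allows restart after more than 14 days with the medical monitor's written permission under three conditions, and reaching 45 is not one of them. Relaxing the level would trade away a safety margin.

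**Conclusion.** The point holds as a minor error, wrong as written. The Grade 1/2 row prints five times the dexamethasone of the Grade 3 row (2.5 against 0.5 mg per rinse; 7.5 against 1.5 mg/day). The daily figures are rinse content, not absorbed dose.

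The five-fold ratio rests on the printed text alone. That the Grade 1/2 row is the more common one rests on Phase 1 experience carrying over at least in direction. That the cause is a dropped 5 is inference. Because the text here was extracted by a program, the digit should be checked against the source PDF first, although loss of a single character in an otherwise intact line would be unusual.

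No endpoint, error rate, power calculation or study-drug dosing rule is affected.

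**What to change.** Ask the clinical team to confirm the intended strength, then print one concentration in both stomatitis rows of Table 7, presumably 0.5 mg/5 mL. If a stronger rinse at Grade 1/2 was in fact intended, state the reason beside the row.

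The cost is one line of text, with no new procedure, data item or analysis. As the SAP records early closure, the correction belongs in the protocol record and in any later protocol that reuses the table.
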